For the definition of pCS high and pCS low, see Section 13.2.2.

Lower Extremity Function Scale (LEFS)

The LEFS will be assessed at the following time points: at 6, 12 weeks and months 6, 12, 18 and 24 after wound closure. It consists of 20 items which can each be answered on a scale of 0 to 4. In the database the answers will be coded as 1 to 5. Therefore, the total LEFS for a patient will be computed as

$$LEFS = \sum_{i=1}^{20} a_i - 20,$$

where a_i is the answer to item i (coded 1 to 5). As indicated in Section 10.1.4.4, the calculation of the total score will be made if less than or equal to 10% of the items were left blank. If more than 10% of items are missing the score cannot be calculated. In the event of missing

items, the total score will be adjusted by dividing the total by the proportion of completed items, as follows:

$$LEFS = \frac{\sum_{i=1}^{k} a_i}{k/20} - 20$$

where k is the number of completed items and a_i are the non-missing values.

Disabilities of the Arm, Shoulder and Hand (QuickDASH)

The QuickDASH will be assessed at the following time points: at 6, 12 weeks and months 6, 12, 18 and 24 after wound closure. It consists of 11 items which are scored 1-5. As indicated in Section 10.1.4.4, the calculation of the total score will be made if less than or equal to 10% of the items were left blank. If more than 10% of items are missing the score cannot be calculated. Hence, at least 10 of the 11 items must be completed for a score to be calculated. The assigned values for all completed responses are simply summed and averaged, producing a score out of five. This value is then transformed to a score out of 100 by subtracting one and multiplying by 25. Hence, the QuickDASH score for a single patient is calculated by:

$$QuickDASH = \left(\frac{sum\ of\ n\ responses}{n} - 1\right) * 25.$$

Range of Motion (ROM)

For each visit (12 months FU and 24 months FU), a binary (yes/no) variable will be calculated, indicating whether the range of motion assessment for that patient was abnormal or not. The range of motion assessment will be considered abnormal, if the measurement of at least one joint under consideration does not lie within the normal ranges of motion given in appendix 13 of the study protocol at the respective time point. For handling of missing data see Section 10.1.4.4.

EQ-5D (Quality of Life)

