All variables not mentioned explicitly in the following will be analyzed descriptively (as part of the case-wise listing).

Unless otherwise specified, all statistical tests will be conducted against a two-sided alternative hypothesis, employing a significance level of 0.05.

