11.1.5.15. Lower Extremity Function Scale (LEFS)

The analysis of LEFS is restricted to subjects with at least one TW with lower extremity involvement. The LEFS scores at 12 months follow up assessment will be presented by treatment group using descriptive statistics. The mean LEFS scores between treatment groups will be compared by a one-way analysis of variance.

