The formula for total number of events D is: $D = \frac{4(z_{\alpha} + z_{\beta})^2}{(\ln \lambda)^2}$

(Piantadosi, Clinical Trials: A Methodologic Perspective, p.169)

 $z_{\alpha} = 1.96$;

 z_{β} = 1.28 for 90% power.

If the proportion of events in NexoBrid group is denoted by $p_1 = 0.64$

and the proportion of events in SoC group is denoted by $p_2 = 0.56$,

which are the observed proportions in the study MW2004-11-02, the number of subjects to be enrolled to achieve a power of 90% for the non-inferiority test is $n = \frac{2D}{p_1 + p_2} = 2164$ (1082 in each group).

Estimate based on study MW2010-03-02

Estimated log hazard ratio from study MW2010-03-02 (NexoBrid versus SoC) = 1.56, using a Cox proportional hazards model with shared frailty adjusted for center, age, %TBSA, proportion of the FT area of a patient and number of TWs (1,2,3-4, ≥5).

Standard error = 0.41

Target log hazard ratio = 1.56 - 0.41/2 = 1.36; target hazard ratio $\lambda = 3.90$.

The formula for total number of events D is: $D = \frac{4(z_{\alpha} + z_{\beta})^2}{(\ln \lambda)^2}$

(Piantadosi, Clinical Trials: A Methodologic Perspective, p.169)

 $z_{\alpha} = 1.96$;

 z_{β} = 1.28 for 90% power.

If the proportion of events in NexoBrid group is denoted by $p_1 = 0.62$

and the proportion of events in SoC group is denoted by $p_2 = 0.73$,

which are the observed proportions in the study MW2010-03-02, the number of subjects to be enrolled to achieve a power of 90% for the non-inferiority test is $n = \frac{2D}{p_1 + p_2} = 34$ (17 in each group).

Cosmesis and Function: MVSS at 12 months

Estimate based on study MW2004-11-02

Estimated difference in MVSS at 24 months from previous study (NexoBrid vs. SoC) = 3.32 - 3.83 = -0.51.

Standard error = 0.50

Target difference $\Delta = -0.51 + 0.50/2 = -0.26$.

The formula for the number of patients per group n is: $n = \frac{2(z_{\alpha} + z_{\beta})^2 \sigma^2}{q(\Delta - d_0)^2}$

where

 $z_{\alpha} = 1.96$;

 z_{β} = 1.28 for a power of 0.9;

 σ = the estimated common standard deviation= 2.33 (taken from previous study);

 d_0 = clinical equivalence level = 1.9;

q = proportion who are retained in follow-up to 12 months = 0.7 (assuming 30% loss to follow-up over 1 year)

For 90% overall power, the required sample size per group is 35 (70 overall).

Estimate based on study MW2010-03-02

Estimated mean MVSS at 12 months from study MW2010-03-02: NexoBrid 3.70; SoC 5.08

Standard errors: NexoBrid 0.24; SoC 0.38

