Difference: -1.38; Standard error of difference: 0.44

Anticipated difference: -1.38 + 0.44 / 2 = -1.16

The non-inferiority margin employed for this analysis is 1.9 score points.

Using a one-sided two-sample t-test with a significance level of 2.5%, 36 evaluable subjects are needed (18 in each group) to achieve a power of 90%. Using a conservative rate of missing values of 30%, the total sample sizes needed to achieve a power of 90% in the analysis is 52 (26 per group).

Note: In the analysis missing data will be imputed, leading to more evaluable subjects, increasing the power.

Cosmesis and Function: MVSS at 24 months

Estimate based on study MW2004-11-02

Estimated difference in MVSS at 24 months from previous study (NexoBrid vs. SoC) = 3.32 - 3.83 = -0.51.

Standard error = 0.50

Target difference $\Delta = -0.51 + 0.50/2 = -0.26$.

The formula for the number of patients per group n is: $n = \frac{2(z_{\alpha} + z_{\beta})^2 \sigma^2}{q(\Delta - d_0)^2}$

where

 $z_{\alpha} = 1.96$;

 z_{β} = 1.28 for a power of 0.9;

 σ = the estimated common standard deviation= 2.33 (taken from previous study);

 d_0 = clinical equivalence level = 1.9;

q = proportion who are retained in follow-up to 24 months = 0.5 (assuming 50% loss to follow-up over 2 years)

For 90% overall power, the required sample size per group is 49 (98 overall).

Estimate based on study MW2010-03-02

Since at this time the 24 months MVSS data of the MW2010-03-02 study is not yet available, the 12 months data will be used for the calculation.

Estimated mean MVSS at 12 months from study MW2010-03-02: NexoBrid 3.70; SoC 5.08

Standard errors: NexoBrid 0.24; SoC 0.38

Difference: -1.38; Standard error of difference: 0.44

Anticipated difference: -1.38 + 0.44 / 2 = -1.16

The non-inferiority margin employed for this analysis is 1.9 score points.

Using a one-sided two-sample t-test with a significance level of 2.5%, 36 evaluable subjects are needed (18 in each group) to achieve a power of 90%. Using a conservative rate of missing values of 50%, the total sample sizes needed to achieve a power of 90% in the analysis is 72 (36 per group).

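### Long-term function, quality-of-life and POSAS comparisons use only children scored at the tested visit; a repeated-measures model would use the other visits at little cost

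*SAP*

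**What the plan says.** **Analyses.** SAP 11.1.5.15 (12 months) and 11.2.4.6 (24 months) analyse the lower-limb score in the same words: "The mean LEFS scores between treatment groups will be compared by a one-way analysis of variance". The same one-way ANOVA is given for QuickDASH (11.1.5.16, 11.2.4.7) and for EQ VAS and the EQ-5D index (11.1.5.18, 11.2.4.9). The index also gets a linear regression on that visit's value. POSAS is compared by a one-way ANOVA at each visit: 6 and 12 weeks and 6 and 12 months in stage 1 (11.1.6.7), 18 and 24 months in stage 2 (11.2.5.1).

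**Missing data.** For LEFS, QuickDASH and POSAS, Sections 10.1.4.4 and 10.1.5.1 deal with missing items only. Missing EQ-5D values are not imputed and form their own category, which can serve the tables of the five items but not an ANOVA of the VAS or index. Sections 10.2 (withdrawals) and 10.5.1 (COVID-19) refer back to 10.1.

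**Data available.** "The LEFS will be assessed at the following time points: at 6, 12 weeks and months 6, 12, 18 and 24 after wound closure". QuickDASH has the same schedule, and the protocol synopsis places cosmesis, function and quality-of-life assessments at those six visits.

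**Contrast.** Missing 12- and 24-month MVSS values are predicted by regression from the last earlier visit, with best- and worst-case analyses added (10.1.4.2). Range of motion uses last observation carried forward (10.1.4.4).

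**Loss rates.** The only ones for long-term follow-up are in the MVSS calculations of Section 13.3: "assuming 30% loss to follow-up over 1 year" and "assuming 50% loss to follow-up over 2 years".

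**The concern.** The SAP never says that these are observed-case analyses, but that is what a single-visit ANOVA without a missing-visit rule amounts to. It compares arms fairly only if, within each arm, having a score at the visit is unrelated to what the score would have been. Attendance one or two years after a burn could well depend on how the child is doing, and the scores from other visits carry information on that. They play no part in the 12- or 24-month comparison. For POSAS they are analysed, but each visit alone.

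At stake are the accuracy and precision of the long-term function, quality-of-life and scar comparisons. The SAP gives no reason for treating these scores differently from MVSS and range of motion, which share the follow-up schedule.

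**Working it through.** **1. Reproduce the figures that carry the loss rates** (Section 13.3, MVSS, estimates from MW2004-11-02). Inputs: z values 1.96 and 1.28, SD 2.33, target difference −0.26, margin 1.9, retention q = 0.7 at 12 months and "q = proportion who are retained in follow-up to 24 months = 0.5".

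n per group = 2(1.96 + 1.28)² × 2.33² / [q(−0.26 − 1.9)²] = 113.98 / (q × 4.6656)

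- q = 0.7: 34.9, so 35 (SAP: 35)
- q = 0.5: 48.9, so 49 (SAP: 49)

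**2. Apply those rates to the 145 children enrolled.**

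- 12 months: 145 × 0.7 = 101.5 scored, 43.5 not
- 24 months: 145 × 0.5 = 72.5 scored, 72.5 not

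At these rates the counts are upper limits for some scores. LEFS and QuickDASH at 12 months are restricted to children with a target wound in the relevant limb. EQ-5D is not assessed below age 2, and 45 of the 145 were enrolled at 0–23 months.

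**3. Precision from one earlier visit.** With loss m, correlation ρ and random loss, the variance relative to the single-visit comparison is 1 − mρ². The documents give no ρ, so 0.3 to 0.7 is assumed. Equivalent complete children = 145(1 − m)/(1 − mρ²).

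| Loss | ρ | Variance ratio | Reduction | Equivalent children |
|---|---|---|---|---|
| 30% | 0.3 | 0.973 | 2.7% | 104 (from 101.5) |
| 30% | 0.5 | 0.925 | 7.5% | 110 |
| 30% | 0.7 | 0.853 | 14.7% | 119 |
| 50% | 0.3 | 0.955 | 4.5% | 76 (from 72.5) |
| 50% | 0.5 | 0.875 | 12.5% | 83 |
| 50% | 0.7 | 0.755 | 24.5% | 96 |

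In power (simulated; 100 children and a true difference of 0.5 SD assumed), correlation that decays between visits from 0.5–0.7 gives 55% rising to 57–59% at 12 months and 42% rising to 44–47% at 24 months. Equal correlation between all visits gives more, 6–13 points, but that assumption is favourable.

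**4. Bias if loss depends on the earlier score equally in both arms.** Assumed: true harm −0.5 SD, present at the earlier visits too; log-odds of loss 1 per SD of earlier score; ρ 0.5–0.7. Simulations with 100 children give shrinkage of about 6–11%. A large-sample check gives −0.47 and −0.45 at 30% loss and −0.46 and −0.44 at 50% loss: (0.50 − 0.47)/0.50 = 6% to (0.50 − 0.44)/0.50 = 12%, the same within rounding. With no true effect the bias is zero.

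**5. Bias if loss depends on the earlier score in one arm only** (no true effect, random loss in the other arm, slope as above, 73 versus 72 children, two-sided test "employing a significance level of 0.05").

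| Loss | ρ | False difference (SD) | Type I error, ANOVA |
|---|---|---|---|
| 30% | 0.3 / 0.5 / 0.7 | 0.07 / 0.13 / 0.18 | 6.7% / 8.9% / 14.3% |
| 50% | 0.3 / 0.5 / 0.7 | 0.12 / 0.21 / 0.29 | 8.5% / 13.8% / 25.4% |

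With the earlier score in the model, type I error is 4.95–5.4% throughout.

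**The case against.** - **The loss rates are borrowed.** They are MVSS planning values, and the calculations from MW2010-03-02 call them conservative ("Using a conservative rate of missing values of 30" per cent, and likewise the 50% rate). The COVID-19 memo (Section 13.4) let the questionnaires be completed by mail, email, phone or video, and POSAS observer scores be taken from photo or video, so actual loss may be lower. This stands.
- **Earlier scores may predict little.** Section 10.1.4.2 says early MVSS values are not considered predictive of late ones. If that held for these scores, the gain would be near the ρ = 0.3 rows. The SAP nevertheless imputes late MVSS from earlier visits.
- **A reader might infer that the ANOVAs could hide harm from NexoBrid or produce a false benefit.** That needs poorly recovering children to leave the NexoBrid arm in particular. Nothing in the documents suggests this. Step 5 shows what such loss would do, not what to expect.
- **A reader might also infer that earlier data are ignored altogether.** For POSAS this is wrong: every visit is compared, only not jointly.
- **The outcomes are secondary in rank.** They are additional safety or exploratory outcomes outside the hierarchy in 11.1.9, and 11.2.8 calls all stage 2 testing exploratory. MVSS already has a missing-data method. This limits the priority.
- **An unstructured model over six visits may not converge** in a subset of unknown size. The fix must allow for that.

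Protocol Section 15.8.4, to which the synopsis refers for missing values, is not in the supplied text. A rule there cannot be excluded, but the SAP carries none over.

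**Conclusion.** The point holds as a modest improvement. Each comparison of LEFS, QuickDASH, EQ VAS, the EQ-5D index and POSAS rests on children scored at that visit, without help from the other visits.

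Under loss that works alike in both arms, the cost is a slightly diluted difference (roughly 6–11%) and some lost precision, with no false effect under the null. A bias of about 0.1–0.3 SD needs arm-specific loss. The power gain from a joint model is a few points if correlation decays over time. Correlations, loss mechanism and subset size are assumptions, and 30% and 50% are planning values for another score. The primary and secondary efficacy conclusions are unaffected.

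**What to change.** Analyse LEFS, QuickDASH, EQ VAS, the EQ-5D index and POSAS with a mixed model for repeated measures over all long-term visits to date:

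- fixed effects for treatment, visit and treatment by visit, plus the stratification factors, with center grouped by region as in 11.1.8;
- unstructured covariance within child, with a simpler structure named in advance in case of non-convergence;
- the 12-month difference reported in stage 1 and the 24-month difference in stage 2, each with a 95% confidence interval;
- the observed-case ANOVA kept as a supportive analysis.

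The cost is SAP wording, standard SAS code and a little more modelling work; no new data are needed. The model assumes that loss is explained by observed scores and covariates (missing at random). This can fail, but it is weaker than what the single-visit ANOVA assumes. A child with no score at any visit still contributes nothing.

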11.1.5.16. Disabilities of the Arm, Shoulder and Hand (QuickDASH)

The analysis of QuickDASH is restricted to subjects with at least one TW with arm, shoulder or hand involvement. The QuickDASH scores at 12 months follow up assessment will be

presented by treatment group using descriptive statistics. The mean QuickDASH scores between treatment groups will be compared by a one-way analysis of variance.

The ROM will be evaluated using a variable with 2 levels (all measurements normal / at least one abnormal finding). Summary tables will be provided giving sample size, absolute and relative frequency and 95% CI (Confidence Interval) for the proportion with a normal score, separately for each study treatment group.

A logistic regression model will be applied for testing the statistical significance of the difference in ROM measurements between NexoBrid and SoC treatments at 12 months. Adjustment will be made for any imbalance between the groups in treatment center, overall treated %TBSA and % of FT per patient.

Only subjects with joint injury will be regarded for this analysis. A footnote to the results will indicate this.

The 12 months follow up assessment of the EQ-5D will be analyzed as follows.

The EQ-5D consists of 5 items with 3 possible answers each and an EQ visual analogue scale. For each item (Mobility, Looking after myself, Doing usual activities, Having pain or discomfort, Feeling worried, sad or unhappy) the count and percentages of each possible answer will be presented per age group (the analysis will be done per age at randomization) and per treatment group. The difference between treatment groups will be tested using a chi square test (or Fishers' exact test in case of small expected cell counts).

The values of the EQ visual analogue scale (EQ VAS) will be presented by treatment group using descriptive statistics. The mean EQ VAS values between treatment groups will be compared by a one-way analysis of variance.

Additionally, the single summary index will be analyzed analogously as the EQ VAS.

The linear regression model with the single summary index as target variable will be applied for testing the statistical significance of the difference in scores between NexoBrid and SoC treatments at 12 months. Adjustment will be made for any imbalance between the groups in treatment center and overall treated %TBSA.

11.1.5.19. Burn Outcome Questionnaire (BOQ)

The BOQ will be analyzed separately. Its analysis will be detailed in a separate document.

11.1.6. Exploratory Analyses

11.1.6.1. Incidence of surgical Escharotomy procedures on circumferential extremities target wounds

Two analyses will be done for this exploratory endpoint. The number and percentage of circumferential extremities target wounds that went through escharotomy will be presented by treatment group. The proportion of circumferential extremities target wounds that went through escharotomy will be compared between treatment groups using a chi square test (or Fisher's exact test in case of small estimated cell counts).

The number and percentage of patients having at least one circumferential extremities target wound, which went through escharotomy, will be presented by treatment group. The proportion of patients having at least one circumferential extremities target wound which went through escharotomy will be compared between treatment groups using a chi square test (or Fisher's exact test in case of small estimated cell counts). The reference count will be the number of subjects with at least one circumferential extremities target wound.

11.1.6.2. Incidence of reduction in interstitial/compartment pressure in circumferential extremities target wounds

This is a binary (yes/no) variable indicating whether the patient experienced reduction in interstitial/compartment pressure in circumferential extremities target wounds for each target wound and each procedure separately. Rates of patients with this event will be analyzed by displaying counts and percentages by treatment group. The proportion of patients with reduction in interstitial/compartment pressure in circumferential extremities target wounds will be compared between treatment groups using a chi square test (or Fisher's exact test in case of small estimated cell counts).

11.1.6.3. % wound area surgically excised for eschar removal

The % wound area surgically excised for eschar removal per patient (computed as in section 10.3.5.3) will be presented by treatment group using descriptive statistics and compared between groups with a one-way analysis of variance.

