11.1.4.4. Incidence of Autograft in DPT Wounds

This is a binary yes/no variable and the proportion of Deep Partial Thickness TWs that were autografted will be compared (on a wound level). Missing data for the main analysis and for the two sensitivity analyses will be handled by the methods described in Section 10.1.3.4. The comparison of NexoBrid versus SoC will be conducted using logistic regression within the generalized estimating equations (GEE) framework that accounts for within-subject correlation between target wounds. The explanatory variables in the model will include treatment, center, age, %TBSA (wound level), proportion of the FT area of a patient and number of TWs (1,2,3-4, \geq 5). The odds ratio of requiring Autograft for NexoBrid versus SoC will be estimated from the model, as well as 95% confidence intervals and the level of statistical significance.

As sensitivity analysis, the procedure outlined above will be repeated using the PP instead of the FAS as analysis population.

Supportive analyses will include adjustments for baseline variables which are found to be imbalanced, based on the analyses described in Section 11.1.1.

These analyses will only take into account DPT target wounds.

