11.1.5.13. Hospital Readmission Rates

Hospital admission rates will be analyzed on a patient level by displaying counts and percentages by treatment group. The proportion of patients needing readmission to a hospital will be compared between treatment groups using a chi square test (or Fisher's exact test in case of small estimated cell counts).

Furthermore, the number of planned hospital readmissions per patient will be analyzed by displaying counts and percentages by treatment group. The number of planned hospital readmissions per patient will be compared between treatment groups using a chi square test (or Fisher's exact test in case of small estimated cell counts).

Additionally, the number of unplanned hospital readmissions per patient will be analyzed by displaying counts and percentages by treatment group. The number of unplanned hospital readmissions per patient will be compared between treatment groups using a chi square test (or Fisher's exact test in case of small estimated cell counts).

Hospital readmission will also be analyzed on a readmission level. Counts and percentages of planned/unplanned readmissions will be displayed by treatment group. The proportion of planned/unplanned readmissions to hospitals will be compared between treatment groups using a chi square test (or Fisher's exact test in case of small estimated cell counts).

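### The wound-level escharotomy test and the readmission-level planned/unplanned test ignore correlation within a child, so their error rate is not the nominal 5%; exploratory and safety reporting only

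*SAP*

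**What the plan says.** SAP 11.1.6.1 plans two analyses of escharotomy on circumferential extremity wounds and does not say which is the main one.

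- **By wound:** "The proportion of circumferential extremities target wounds that went through escharotomy will be compared between treatment groups using a chi square test". When counts are small, the fallback is Fisher's test.
- **By patient:** children with at least one escharotomised circumferential wound are compared by the same tests. "The reference count will be the number of subjects with at least one circumferential extremities target wound".

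SAP 11.1.5.13 has the same two layers for readmission.

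- **By patient:** "The proportion of patients needing readmission to a hospital will be compared between treatment groups using a chi square test". The numbers of planned and of unplanned readmissions per patient are also compared. Fisher's test is the fallback throughout.
- **By readmission:** "The proportion of planned/unplanned readmissions to hospitals will be compared between treatment groups using a chi square test", again with Fisher's test as the fallback.

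Allocation is by child, 1:1, using minimisation on patient-level factors (SAP 11.1.11 and 13.1). For another binary outcome analysed by wound, autograft in deep partial thickness wounds, SAP 11.1.4.4 specifies "logistic regression within the generalized estimating equations (GEE) framework that accounts for within-subject correlation between target wounds".

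**The concern.** A chi-square or Fisher test assumes that every unit in the table is independent. Two burned limbs of one child share the patient, the surgeon, the centre and the allocated treatment. Repeated readmissions of one child share much the same. When such units are positively correlated within children and allocation is by child, the variance of the difference between arms is larger than the test assumes.

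The readmission-level test has a second problem that does not depend on any correlation. It compares the planned/unplanned mix among readmissions that took place. Whether a child is readmitted, and how often, is itself an outcome, so randomisation does not protect the comparison. If one arm had fewer planned readmissions and the same number of unplanned ones, its unplanned share would rise although no child had fared worse.

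At stake is the reading of two p-values. Avoiding escharotomy is among the product benefits listed in SAP 2.1, and the hospital readmission rate is a safety measure (Protocol synopsis, Safety Outcome Measures; SAP 7.2.3.6). Since 11.1.6.1 names no main analysis, the wound-level p-value could be quoted beside the patient-level one or in its place.

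**Working it through.** **1. How the SAP treats several units per child**

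| Analysis | Unit | Allowance for the child |
|---|---|---|
| Eschar removal, additional (11.1.3) | wound | marginal Cox with robust variance, or frailty |
| Surgical excision, additional (11.1.4.1) | wound | random patient effect |
| Area of autograft, additional (11.1.4.3) | wound | random patient effect |
| Incidence of autograft (11.1.4.4) | wound | GEE |
| Wound closure (11.1.5.1) | wound | marginal Cox with robust variance, or frailty |
| Incidence of autograft in age subgroups (11.1.12.1) | wound | GEE |
| Escharotomy (11.1.6.1) | wound | none |
| Planned/unplanned (11.1.5.13) | readmission | none |

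The plan expects several units per child. Target wounds are grouped as 1, 2, 3-4 and ≥5 (10.3.2), and planned and unplanned readmissions are counted for each patient (10.3.4.4).

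**2. Inputs**

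- Stated level: "Unless otherwise specified, all statistical tests will be conducted against a two-sided alternative hypothesis, employing a significance level of 0.05" (SAP section 11, repeated in 11.1.9). No other error rate is given for these tests, so there is no further figure to reproduce.
- Not stated anywhere: the ICC, the number of circumferential wounds or readmissions per child, and the event rates. Assumed ranges are ICC 0.3 to 0.8, one to three units per child, and event rates from 3% upward.

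**3. Large-sample error rate**

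Design effect DE = 1 + (m − 1) × ICC. Actual level = 2 × [1 − Φ(1.96/√DE)].

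| Units per child | ICC 0.3 | ICC 0.5 | ICC 0.8 |
|---|---|---|---|
| m = 1 | 0.050 | 0.050 | 0.050 |
| 80% with one, 20% with two | 0.062 | 0.070 | 0.082 |
| m = 2 | 0.086 | 0.110 | 0.144 |
| m = 3 | 0.121 | 0.166 | 0.224 |

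Example: m = 2 and ICC 0.5 give DE = 1.5, 1.96/√1.5 = 1.600, level 0.110. For the mixed row the size-weighted m is (0.8×1 + 0.2×4)/(0.8×1 + 0.2×2) = 1.6/1.2 = 1.33, so DE is 1.10, 1.17 and 1.27.

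**4. Effect of the Fisher fallback**

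The formula ignores Fisher's test, so the rule was simulated under no treatment difference: beta-binomial data, 4000 runs per cell, and Fisher's test when an expected count is below 5. That threshold is an assumption; the SAP gives none.

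| Scenario | ICC 0.3 | ICC 0.5 | ICC 0.8 |
|---|---|---|---|
| 20 children/arm, 80% one and 20% two units, 30% events | 0.056 | 0.068 | 0.079 |
| 20/arm, two units, 30% events | 0.080 | 0.109 | 0.152 |
| 20/arm, two units, 10% events | 0.050 | 0.069 | 0.098 |
| 20/arm, two units, 3% events | 0.005 | 0.006 | 0.014 |
| 40/arm, two units, 3% events | 0.019 | 0.031 | 0.049 |
| 40/arm, three units, 3% events | 0.062 | 0.098 | 0.164 |

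The simulation agrees with the formula when events are common. With rare events the level is often below 5%, but not always.

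**5. What a larger inflation would need**

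A level of 0.10 needs DE = (1.96/1.645)² = 1.42, which is ICC 0.42 at m = 2 or 0.21 at m = 3. A level of 0.15 needs DE = (1.96/1.440)² = 1.85, which is ICC 0.85 at m = 2 or 0.43 at m = 3.

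**The case against.** The strongest reply has four parts.

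- **Valid tests are already planned.** Both sections include comparisons with one observation per child, and how often children have unplanned readmissions is tested per patient. This stands, and it makes the fix easy.
- **Nothing confirmatory is involved.** Escharotomy is exploratory, readmission is an additional safety measure, and the hierarchy in SAP 11.1.9 holds only the primary and four secondary endpoints. This stands and limits the weight of the point. It does not excuse the method: the age subgroups in 11.1.12 are also labelled exploratory and still use GEE for autograft by wound.
- **Fisher's test limits the inflation.** Partly right. With rare events the simulated level often falls below 5%. But Fisher's test also assumes independent units; its conservatism offsets the correlation by accident and does not model it.
- **GEE may not fit.** This stands. With two wounds per child, ICC 0.5 and a 10% event rate, the beta-binomial probability that a child has no event is 0.9×1.9/2 = 0.855. With 10 children per arm, at least one arm is then empty of events with probability 1 − (1 − 0.855^10)² = 0.37; with 20 per arm, 0.09. A logistic odds ratio cannot be estimated in those cases.

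A reader might also infer that the compartment-pressure comparison in 11.1.6.2 is a clustered test, because its variable is defined "for each target wound and each procedure separately". The documents do not support that. The same paragraph names the proportion of patients as the quantity compared. The wording leaves open how wounds and procedures become one value per patient, but it does not show a test that counts wounds as independent. Pressure is not part of this point.

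**Conclusion.** The point holds for two tests: escharotomy by wound and planned/unplanned status by readmission. Both ignore correlation within a child, contrary to the SAP's own practice for other wound-level outcomes, and the second also has a post-randomisation denominator.

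The size is conditional. The false-positive rate is about 9% to 14% at two units per child with ICC 0.3 to 0.8 if events are not rare. It is about 6% to 8% if most children have one unit, and possibly below 5% if events are rare and Fisher's test applies. All of this rests on assumed ICC, cluster size and event rate.

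A reader might infer that the plan doubles or triples the false-positive rate. The documents do not establish that. It would need ICC of about 0.42 to 0.85 at two units per child, or 0.21 to 0.43 at three, with events that are not rare, and none of these quantities is given. The effect is confined to exploratory and safety reporting.

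**What to change.** - In 11.1.6.1 and 11.1.5.13, state that the patient-level tests already planned are the only inferential ones.
- Present escharotomy by wound and planned/unplanned by readmission as counts and percentages by arm, without a p-value.
- If a wound-level test of escharotomy is still wanted, use the GEE approach of 11.1.4.4, on condition that events are frequent enough in both arms to fit it; otherwise report descriptively.
- Do not replace the readmission-level test with a cluster-adjusted one, since adjustment would not repair the post-randomisation denominator.

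The cost is a few lines of SAP text and the loss of two exploratory or safety p-values. No new data or endpoint is needed, and the primary and secondary analyses are unchanged.
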